Bwrdd Iechyd Prifysgol
Hywel Dda
University Health Board

Research Protocol (Version 1.4, 21/03/2024)

Study Title: A cross-sectional study assessing the agreement between sonographer based assessment of the fatty liver using conventional ultrasound and attenuation imaging scoring.

Acronym/Short Title: Ultrasound and Attenuation Imaging

Study ID (IRAS No.): 329847

REC Reference:23/WA/0332

Protocol Version No. & date: (Version 1.4, 21/03/2024)

Author(s) & Designation(s): [name], Sonographer, Researcher

Study Summary

Study Outline	Non-alcoholic fatty liver disease (NAFLD) affects almost a 3 rd of the population of the UK and current best practice is to evaluate this using Magnetic Resonance Imaging proton density fat fraction (MRI PDFF), however, this is inaccessible to many patients due to limited availability, cost and a large exclusion criteria. Ultrasound offers an affordable, faster and more inclusive method of liver evaluation but only subjective assessment of fatty liver disease until a recent development- Attenuation Imaging. Attenuation imaging gives a numerical score for fatty liver disease. Attenuation imaging has previously only been compared to MRI PDFF, however, when many patients do not have MRI PDFF it is essential to compare it to common practice, conventional ultrasound. This study aims to assess the agreement between conventional ultrasound assessment of the liver and attenuation imaging using a cross-sectional method. Convenience sampling will be used to select 95 participants who will have their attenuation imaging score carried out alongside their routine ultrasound scan with the sonographer blinded to the attenuation imaging results. The inter-rater agreement will be determined using Kappa statistics. The results will demonstrate the strength of relationship between the two methods. A strong agreement between the two may facilitate further investigation into the uses of attenuation imaging, such as use as a screening tool, in teaching trainee ultrasound operators or in aiding decisions in cases that Sonographers find more difficult to assess such as those patients with a high BMI.
Lay Summary	Fatty liver disease affects almost a 3rd of the UK population. Currently, this is being investigated using a type of Magnetic Resonance Imaging (MRI) scan that reports how fatty or not a person's liver is, with a liver fat score, but many patients cannot have this type of scan due to time, cost or because they have a condition which makes MRI an unsafe scan for them to have. An ultrasound scan is cheaper, faster and safer for a wider variety of patients. New developments in ultrasound technology mean that instead of a Sonographer, or ultrasound operator, deciding whether your liver is fatty or not based on what they see on the scan, the ultrasound machine gives a liver fat score. This study will look at the relationship between the Sonographers' view on how fatty the liver is, compared with the liver fat score given by the new development in ultrasound technology.
Key Words	'Ultrasound' 'Non-alcoholic Fatty Liver Disease' 'Metabolic Liver Disease' 'Attenuation Imaging'
Objectives	To assess the agreement between Sonographer based ultrasound assessment of fatty liver disease and attenuation imaging scoring.
Sample Size	95
Duration	1 year

Glossary / Definitions / Acronyms

EASL

European Association for the Study of the Liver

GDPR	General Data Protection Regulation
HDUHB	Hywel Dda University Health Board
IRAS	Integrated Research Application System
MRI	Magnetic Resonance Imaging
MRI-PDFF	Magnetic Resonance Imaging- Proton Density Fat Fraction
NAFLD	Non-alcoholic Fatty Liver Disease
NHS	National Health Service
NICE	National Institute for Health and Care Excellence
PIS	Participant Information Sheet
R&D	Research and Development
REC	Research Ethics Committee

Statement of Compliance

The study as detailed within this Protocol (Version 1.4, 21/03/2024) or any subsequent amendments will be conducted in accordance with the International Conference for Harmonisation of Good Clinical Practice (ICH-GCP, E6), and the UK Policy Framework for Health and Social Care Research (2017), the World Medical Association Declaration of Helsinki (1996) and the current applicable regulatory requirements and any subsequent amendments of the appropriate Regulations.

Signature Page

1.1. Background

Magnetic Resonance Imaging Proton Density Fat Fraction (MRI PDFF) is recommended by the European Association for the Study of the Liver as the gold standard for assessing fatty liver disease (EASL et al., 2016). MRI PDFF gives a complete evaluation of the liver enabling assessment for other pathology and quantification of the fatty infiltration for segments of the liver. MRI is non-invasive but expensive, with multiple exclusion criteria, long waiting times and limited availability (Gatos et al., 2022). Most MRI scanners are unsuitable for patients with a larger body habitus (Reynolds, 2011), who would naturally make up a significant proportion of those with NAFLD due to its causative factors- most commonly poor diet and lack of exercise. They are also poorly tolerated by patients due to noise and claustrophobia. In addition, it excludes patients with artificial heart valves, recent surgery or dental work, and internal electronic devices such as pacemakers or insulin pumps (Medicines and Healthcare Products Regulatory Agency, 2021). Insulin pumps are a particular issue for this population as there is a 53% prevalence of NAFLD within the type 2 diabetic population (NICE, 2016).

Ultrasound is recommended as a first-line test for NAFLD (EASL et al., 2016). It is easily accessible, well tolerated by most patients, more cost-effective than MRI, gives a complete overview to assess for other liver pathology and is non-invasive (Ballestri et al., 2021). However, conventional ultrasound relies on a subjective liver assessment by the operator, which research shows is open to inter-observer variation (Straus et al., 2007) and image quality can also be limited by patient obesity (Reynolds, 2011). It also has a low detection rate of mild steatosis, or steatosis involving less than 30% of the liver parenchyma (Ballestri et al., 2021). In current practice, sonographers grade the fatty appearance of the liver subjectively as normal, mild, moderate or severe through assessment of the echogenicity of the liver, hepato-renal contrast, visualisation of the intra-hepatic veins and visualisation of the liver parenchyma (Hernaez et al., 2011, Ballestri et al. 2021). Ultrasound is also recommended for monitoring those with advanced fatty liver disease, where there are often fibrotic changes with progression to cirrhosis and an increased risk of hepatocellular carcinoma (EASL et al., 2016).

A new advance in ultrasound technology, attenuation imaging, permits quantitative measurement of liver fat, which poses no additional risk to the patient than regular ultrasound and can be carried out as a part of a routine ultrasound scan (Bae et al., 2019). As attenuation imaging is not hindered by the subjectivity of conventional ultrasound assessment, it has potential as a more specific way to monitor the progress of fatty liver disease and to aid more inexperienced sonographers as an adjunct to their subjective assessment. Most of the literature compares attenuation

imaging to MRI-PDFF as the gold standard, and multiple studies suggest that attenuation imaging has reasonable specificity and sensitivity (Ferraioli et al., 2021, Jeon et al., 2019). However, as previously stated, MRI is not suitable for an extensive range of patients and long waits for MRI scans and reports make it unfeasible as a method of choice for assessing and monitoring the fatty liver locally, especially in the early stages when the risk of hepatocellular carcinoma is much lower. Consequently, whilst the literature compares attenuation imaging to MRI PDFF, as the gold standard, it is essential to evaluate the use of attenuation imaging against current ultrasound practice, which at this location is a more common method of liver evaluation than MRI PDFF. Furthermore, this study will provide a base of evidence to allow further research in the future to find answers to questions such as 'How does knowing these scores affect patients attitudes to treatment?' or 'At which stage is treatment most effective?'.

1.2. **Research Question**

What is the level of agreement between sonographer based assessment of the fatty liver using conventional ultrasound and attenuation imaging scoring?

2. Study Outline

2.1. **Aims and Objectives**

Evaluate the agreement between a sonographer-based assessment of the fatty liver using conventional ultrasound and attenuation imaging scoring.

Describe any disagreement between sonographer-based assessment of the fatty liver and attenuation imaging scoring.

Assess if there is any variation in agreement at different grades of fatty liver disease.

2.2. **Method**

2.2.1. **Study Type**

This study will be carried out using a cross-sectional quantitative methodology.

2.2.2. **Study Overview**

A cross-sectional design will be used for this study. The Sonographer appraisal and attenuation imaging score will be collected from observations made at a single point in time during the ultrasound scan to look at the agreement between the two factors. These features, data collected through the sample being observed at a single point in time to assess agreement, make this an appropriate design for this study (Ellis, 2019). Evidence of agreement may point towards further areas for research such as use as a screening tool or point of care ultrasound. However, as an inexpensive method of collecting and comparing a large quantity of data, a cross-sectional study is a pragmatic choice (McClean, 2020).

The data will be obtained from a population of patients having abdominal or liver scans in Bronglais Hospital, Aberystwyth, until sufficient data has been collected in line with calculated sample size. Establishing criteria for inclusion and exclusion allows exclusion of patients who may be clinically unsuitable or unable to consent. The inclusion and exclusion criteria with justification for these decisions are set out in table 1. Identifying patients eligible for inclusion in the study should be achievable from the assessment of patient referral forms. Most exclusion criteria should also be

detected from the referral form; however, patients with unknown large or multiple liver masses may be identified during the scan. Patients will be informed via the PIS that if it is found for any reason that they do not meet the criteria that they will be informed that this is the case, and we will collect no further data from them. Their care will continue as normal. Patients identified in this way will be excluded from the results.

There will be no randomisation all participants will undergo the same study procedure, which will be carried out during a single, routine hospital visit, avoiding the need for participants to attend additional appointments. The assessment will be carried out by two experienced sonographers with a minimum of 10 years of abdominal scanning experience. Sonographer 1 will scan each participant, with Sonographer 2 reviewing the images later in the same conditions to avoid variation caused by lighting conditions. Both sonographers will be blind to the participant's history before completing the liver assessment to avoid any bias from past medical history. They will assess the liver using routine ultrasound, making their decision based on hepato-renal contrast, visualisation of the walls of the intra-hepatic veins and visualisation of the liver parenchyma (Hernaez et al., 2011, Ballestri et al. 2021). The sonographers will individually grade the liver as normal, mild, moderate or severely fatty, recording this on a case report form. The attenuation imaging function will then be switched on and the ultrasound machine will calculate the attenuation imaging scores, according to manufacturer guidance, which will be recorded on the case report form along with the participant's age, gender, and diagnosis. The BMI measurement will also be taken in the time around the participant's appointment and recorded on the case report form as BMI has an impact on image quality (Reynolds, 2011).

2.2.3. Study Populations, Subject Selection, Recruitment and Study Schedule

Convenience sampling permits all patients scanned in the time frame who meet the inclusion criteria to be included in a study reducing time and cost (Walliman, 2011) making this a realistic choice for this study. However, this type of sampling is not representative of the population, which limits the ability to generalise the findings (Walliman, 2011). This method is widely used in clinical research and convenience sampling at a single site is common in healthcare as data protection issues limit data transport across multiple sites (Kahn et al. 2012).

Eligible patients will be identified in line with the eligibility criteria described below. Informed consent will be obtained from all participants prior to any study procedures. A study schedule and participant flow chart are attached in Appendix 1.

2.2.4. Eligibility Criteria

Hepatic steatosis appears in different sexes at different ages and is linked to obesity and metabolic disease, such as diabetes mellitus (EASL et al., 2016) and so it is important to include this in the study. Large liver masses impede both sonographic assessment and attenuation imaging and so will be excluded. Inpatients will also be excluded as these are often difficult to scan due to poor mobility but also are often too unwell to be in the department for any length of time. Patients with complex anatomy due to congenital or surgical reasons or who due to body type are not suitable for conventional ultrasound will also be excluded. Fatty livers are unusual in the younger population unless drug induced and participants need to be able to

consent so only an adult population will be included. Patients with normal livers will be included as livers can be graded as normal, mild, moderate or severely fatty.

Table 1

Variable	Measure
Age	Inclusion: 18 < years Exclusion: < 18 years
Patient group	Inclusion: GP and OP referrals. Exclusion: Inpatients
Clinical history	Inclusion: NAFLD, Unknown, Diabetes, Other metabolic disease Exclusion: Known large liver mass. Poor visualisation of the liver due to body type or unusual anatomy.

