3.1. Screening Duties

[name], as the researcher and a member of the clinical team, will be responsible for screening potential research participants. All ultrasound requests are vetted for suitability by a Sonographer as part of their clinical role. The researcher will review requests for abdominal scanning during the normal vetting procedure.

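### Does the looser body-type exclusion in Table 1 remove livers that the study needs?

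*Combined protocol and SAP*

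**What the plan says.** The text of section 2.2.4 removes patients with complex congenital or surgical anatomy, and those "who due to body type are not suitable for conventional ultrasound will also be excluded". Table 1, which follows it, lists as an exclusion "Poor visualisation of the liver due to body type or unusual anatomy". Section 2.2.2 directs the reader to the table: "The inclusion and exclusion criteria with justification for these decisions are set out in table 1".

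Section 2.2.4 also says that steatosis "is linked to obesity and metabolic disease, such as diabetes mellitus", "and so it is important to include this in the study". The Study Summary names, as one possible later use of attenuation imaging, "aiding decisions in cases that Sonographers find more difficult to assess such as those patients with a high BMI".

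On procedure, section 3.1 says: "The researcher will review requests for abdominal scanning during the normal vetting procedure". Section 2.2.2 expects most exclusions to be visible on the referral form and allows for a few to emerge at the scan. Section 3.2 ends data collection when measurement proves impossible, names body habitus as one cause, records the reason and keeps the remaining data for a reject analysis. Section 2.2.2 records BMI because it affects image quality. Recruitment runs "until sufficient data has been collected in line with calculated sample size", which is 95.

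**The concern.** On plain meaning, the two body-type wordings set different thresholds. A patient unsuitable for ultrasound would be poorly visualised, but a poorly visualised liver can often still be graded. Since section 2.2.2 points to Table 1, the wider wording could be the one applied.

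The livers affected may not be a random subset. How well the vein walls and parenchyma are seen is part of the grade (section 2.2.2), and the protocol links obesity both to steatosis (section 2.2.4) and to poorer images (section 1.1). An exclusion for poor visualisation could therefore thin out the upper grades and the high-BMI patients. The upper grades matter for the section 2.1 objective on agreement at different grades. High-BMI patients are those whom the Study Summary hopes the technique may later help.

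**Working it through.** **Wording.** The three standards side by side:

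| Place | Body type | Anatomy |
|---|---|---|
| 2.2.4 text | unsuitable for conventional ultrasound | complex anatomy, outright |
| 2.2.4 Table 1 | liver poorly visualised | only if the liver is poorly visualised |
| 3.2 | measurement not possible | not named |

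Table 1 reads as wider for body type and narrower for anatomy, so the net difference in numbers excluded is undetermined. Section 2.2.2 says the reasons for the criteria are in Table 1, but they stand in the text of 2.2.4. That favours reading text and table together.

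**Size.** The plan gives no rate of poor visualisation, no BMI distribution and no grade mix. Apart from N = 95 and linear weighting, every input below is assumed.

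- Latent fat T ~ N(0, 1). The sonographer and attenuation readings are each T plus error of SD 0.35, cut into four grades. Grade mixes are 50/25/15/10% and 70/15/10/5%.
- P(poorly seen | T) = Φ(a + bT), with a set so that the overall share is q = 5, 10 or 18%. Overlap with fat is none (b = 0), moderate (b = 0.5) or strong (b = 1.0).
- A share g = 25, 50 or 75% of the poorly seen can be graded. Sonographer error in them is 1, 2 or 3 times the usual.
- The text rule keeps the poorly seen but gradable; the Table 1 rule drops all the poorly seen.
- κ = (Po − Pe)/(1 − Pe), with weights 1 − |i − j|/3, over 2,000,000 draws.

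Change in kappa, Table 1 rule minus text rule, over all q, mixes and error multiples:

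| g | b from 0 to 0.5 | b = 1.0 |
|---|---|---|
| 25% | −0.009 to +0.018 | −0.030 to +0.001 |
| 50% | −0.016 to +0.033 | −0.049 to +0.004 |
| 75% | −0.021 to +0.046 | −0.061 to +0.008 |

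The standard error of kappa at N = 95 (b = 0.5, g = 50%) is 0.053 to 0.075. For the 50/25/15/10 mix at q = 18%, b = 0.5 and g = 50%, kappa goes from 0.676 to 0.665 with the usual sonographer error and from 0.643 to 0.665 with three times that error. The sign depends on an unknown.

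**Severe livers.** Because recruitment continues to 95, exclusions alter the mix and not N. Expected severe livers among 95, text rule to Table 1 rule, at b = 0.5 and g = 50%:

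| Severe in source population | q = 5% | q = 10% | q = 18% |
|---|---|---|---|
| 10% | 8.9 to 8.4 | 8.6 to 7.6 | 8.2 to 6.7 |
| 5% | 4.4 to 4.0 | 4.2 to 3.6 | 4.0 to 3.0 |

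The differences run from 0.4 (4.4 − 4.0) to 1.5 (8.2 − 6.7). With b = 0 the loss is nil. With b = 1.0 and 10% severe it is 0.5 to 4.0 over all q and g. By-grade precision is poor in any case: 6 of 8 agreeing has an exact 95% interval of 35–97%, and 5 of 7 has 29–96%.

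**Patients who fall between the wordings.** Under the text rule their expected number among 95 is 95 × qg/(1 − q(1 − g)). With g = 50%:

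- q = 5%: 95 × 0.025/0.975 = 2.4
- q = 10%: 95 × 0.05/0.95 = 5.0
- q = 18%: 95 × 0.09/0.91 = 9.4

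Kappa with and without 2 to 9 patients could only be described, not tested.

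**The case for a change.** The strongest case for a change is that one exclusion is stated at three thresholds and the key term is undefined, so who is left out depends on judgement at the scan. A poorly seen patient could follow section 2.2.2 (out of the results, no further data) or section 3.2 (reason recorded, other data kept). The quality that triggers the exclusion overlaps with the quality being graded, and editing the table would cost almost nothing. If overlap with fat is strong, the loss is not trivial: up to 4.0 severe livers in 95. Even at moderate overlap with half gradable, the chance of fewer than five severe livers rises from 0.08 to 0.19 (10% severe, 18% poorly seen).

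The inconsistency stands as a drafting point. The rest is weaker. Table 1 excludes poor visualisation only where body type or anatomy causes it, so veins or parenchyma obscured by fat are not excluded on its wording. Selective loss of severe livers therefore needs a further assumption that the documents do not supply. The unknown grade mix matters more than the exclusion: with nobody excluded, the chance of fewer than five severe livers is 0.03 at 10% severe and 0.48 at 5%. Help for high-BMI patients is a possible later use, not an objective in section 2.1, and section 2.2.3 already says the convenience sample is not representative.

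The obvious repairs also have limits. Excluding only when no grade or no attenuation value can be obtained matches neither wording in 2.2.4 and would be a fresh eligibility choice, open to debate. A tick-box for poor visualisation would carry over the same undefined term.

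**Conclusion.** No change is needed. The two wordings differ, but the point is mainly an undefined term that two sonographers, each with at least 10 years of abdominal scanning, can be expected to apply sensibly. Section 3.2 gives them a working rule for failed measurements. Recording BMI for its effect on image quality implies that scans of varying quality were expected in the sample. No passage tells them to discard a liver they have graded.

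No material harm is shown. At half gradable, every kappa shift is smaller than one standard error and its direction is unknown; only the extreme corner (75% gradable, strong overlap, −0.061) reaches the standard-error range. About 0.4 to 1.5 severe livers of 95 are lost at moderate overlap and none without overlap, while by-grade precision is limited mainly by N = 95 and the grade mix. These figures rest on assumed rates and would be larger under strong overlap.

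Applied literally, Table 1 would still give a sound kappa for adequately visualised livers. Section 3.2 already collects the reasons for failed measurements that a report would need. Aligning the sentences would be tidy editing, but no alternative clearly improves a result.

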2.2.5. Power Calculation

The statistical test to determine inter-rater agreement when data are at the ordinal level is kappa (McHugh, 2012). The degree of agreement ranges between -1 and 1.0; 1.0 infers complete agreement, and 0 less agreement than random chance, with negative values indicating disagreement. Assessment of the strength of agreement will be based on the limits described by Landis and Koch (1977) where ≤ 0 =poor, 0.01–0.20=slight, 0.21–0.40=fair, 0.41–0.60=moderate, 0.61–0.80=substantial, and 0.81–1=almost perfect agreement.

The sample size for kappa is calculated based on the need to detect a difference between levels of agreement. McHugh (2005) acknowledges that an agreement of 0.80 or above is more widely accepted in healthcare as the minimum interrater agreement, and a kappa of 0.59 and below an inadequate agreement. Using these values with a power of 90% and alpha set at 0.05, the sample size will be 95.

